11.3 Quality of Life Assessment

Quality of life will be assessed using the EORTC QLQ-C30 questionnaire and the QLQ-HDC29 module (Appendix G) at the following timepoints:

- EORTC QLQ-C30 questionnaire at the time of screening
- EORTC QLQ-C30 & QLQ-HDC29 at the completion of initial therapy prior to transplant
- EORTC QLQ-C30 & QLQ-HDC29 at 100 (\pm 14) days after stem cell infusion (Day +100)

The QLQ-C30 is a validated and widely used questionnaire to assess quality of life in cancer patients. The QLQ-HDC29 is treatment-specific quality of life questionnaire to QLQ-C30), that addresses treatment-specific side effects as well as emotional, social, and family issues for patients treated with high-dose regimens and HCT. The QLQ-HDC29 module is targeted to cover time during the treatment and up to 6 months post-treatment.

The QLQ-C30 is composed of both multi-item scales and single-item measures. These include five functional scales, three symptom scales, a global health status / quality-of-life scale, and six single items. Each of the multi-item scales includes a different set of items - no item occurs in more than one scale.

All of the scales and single-item measures range in score from 0 to 100. A high scale score represents a higher response level.

When the Quality of Life questionnaires are scored, the principle for scoring these scales is the same in all cases:

1. Estimate the average of the items that contribute to the scale; this is the raw score.
2. Use a linear transformation to standardize the raw score, so that scores range from 0 to 100; a higher score represents a higher ("better") level of functioning, or a higher ("worse") level of symptoms.

The QLQ-HDC29 module includes 29 items, consisting of 6 multi-item scales and 8 single-items. The scoring algorithms are similar to the scoring for the EORTC QLQ-C30. For the multi-item scales and single-item scales (except item 52) a high score is equivalent to worse or more symptoms/problems. For Spiritual item 52, a higher score indicates positive experience or less problems.

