30. How would you rate your overall quality of life during the past week?

1 2 3 4 5 6 7

Very poor

Excellent

EORTC QLQ – HDC29

Patients sometimes report that they have the following symptoms or problems. Please indicate the extent to which you have experienced these symptoms or problems during the past week. Please answer by circling the number that best applies to you.

During the past week:	Not at all	A little	Quite a bit	Very much
31. Have you had soreness in your mouth?	1	2	3	4
32. Have you had a dry mouth?	1	2	3	4
33. Have you had trouble swallowing?	1	2	3	4
34. Did food and drink taste different from usual?	1	2	3	4
35. Have you had abdominal pains or cramps?	1	2	3	4
36. Have you had skin problems (e.g. itchy, dry)?	1	2	3	4
37. Have you been upset by how the treatment has affected your hair?	1	2	3	4
38. Have you worried about your weight being too low?	1	2	3	4
39. Have you had fevers or chills?	1	2	3	4
40. Did you urinate frequently?	1	2	3	4
41. Have you had aches or pain in your bones?	1	2	3	4
42. Have you found it difficult to finish things you started?	1	2	3	4
43. Did you worry about the results of examinations and tests?	1	2	3	4

Please, complete the following questions if you are currently still in hospital for your treatment. If not, please go to question 48 on next page.

During the past week:	Not at all	A little	Quite a bit	Very much
44. Have you had trouble coping with the hospital stay?	1	2	3	4
45. Has the isolation in hospital troubled you?	1	2	3	4
46. Have you worried that the blood (i.e. blood counts) may not recover?	1	2	3	4
47. How satisfied were you with the preparation for your treatment?	1	2	3	4

Please go on to the next page

During the past four weeks:

	Not at all	A little	Quite a bit	Very much
48. Have you felt isolated from those close to you (family, friends)?	1	2	3	4
49. Have you been concerned about disruption to your family life because of your treatment?	1	2	3	4
50. How distressing, do you think, your illness or treatment has been to those close to you?	1	2	3	4
51. Have you felt a need to keep your fears/concerns from family or friends?	1	2	3	4
52. Has your experience helped you to distinguish between important and non-important things in life?	1	2	3	4
53. Were you worried about your health in the future?	1	2	3	4
54. Have you felt physically less attractive as a result of your illness or treatment?	1	2	3	4

Please mark the box, if the next question does not apply to you

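### Section 11.3 names only item 52 as favourable when high and gives no item reversal, so the written steps would score QLQ-HDC29 item 47 (satisfaction) backwards unless it is recoded

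*Combined protocol and SAP*

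**What the plan says.** Section 11.3 (Quality of Life Assessment) gives two general scoring steps. The first is "Estimate the average of the items that contribute to the scale; this is the raw score". The second is "Use a linear transformation to standardize the raw score, so that scores range from 0 to 100", with high meaning better on functioning scales and worse on symptom scales. The QLQ-HDC29 is said to be scored in a similar way to the QLQ-C30. It is described as 29 items in 6 multi-item scales and 8 single items, but the plan does not say which items belong to which scale.

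On direction, Section 11.3 states, for both kinds of scale: "except item 52) a high score is equivalent to worse or more symptoms/problems". The one exception is then explained: "For Spiritual item 52, a higher score indicates positive experience or less problems".

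The form in Appendix G prints item 47 as "47. How satisfied were you with the preparation for your treatment", with the same answers from 1 (not at all) to 4 (very much) as its neighbours. Items 44 to 47 follow the instruction "Please, complete the following questions if you are currently still in hospital for your treatment"; other patients skip to item 48.

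Quality of life is a secondary endpoint (Section 4.2.2). Section 13.0 plans to report absolute scores and to use the standardized response mean for changes over time and differences between groups.

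**The concern.** Items 44 to 46, the rest of the in-hospital block, ask about trouble or worry, so a high answer is bad. Item 47 asks about satisfaction, so a high answer is good. Section 11.3 deals with a favourable item by naming it as an exception, and it names only item 52. An analyst working from that section has no instruction to treat item 47 differently from the problem items around it.

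At stake is the meaning of one reported item or of one multi-item scale. If item 47 is reported alone, its score would be read in the opposite sense to the patient's answer. If it is averaged with problem items, it would pull the scale the wrong way, and the scale score would then mix two directions. Only patients in hospital answer the item and there are 30 patients per arm, so responses may be few and a sign error could go unnoticed.

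**Working it through.** No sample size or power figure bears on this point, so the check applies the written scoring steps directly.

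**Inputs**
- Answers 1 to 4, and the wording of item 47: Appendix G.
- Average, then linear transformation to 0–100, with high meaning worse except for item 52: Section 11.3.
- Scale membership of item 47: not given. It is taken below as standing alone, or as one of *k* = 2, 3 or 4 items (assumption).

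**Consistency of the form with the text.** Items 31 to 59 give 59 − 31 + 1 = 29 items, as Section 11.3 states. Taking out 8 single items leaves 21 items in 6 multi-item scales, 3.5 on average, so 2 to 4 items is a reasonable range for illustration.

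**Formula.** For items answered 1 to 4, with high meaning worse: score = (mean − 1) / 3 × 100.

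**Item 47 alone**

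| Answer | As written | Reversed first (5 − answer) |
|---|---|---|
| 1, not at all satisfied | 0 | 100 |
| 2 | 33.3 | 66.7 |
| 3 | 66.7 | 33.3 |
| 4, very much satisfied | 100 | 0 |

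Under the stated direction rule, the left-hand scores label the most satisfied patient as the worst off.

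**Item 47 in a scale of *k* items.** Take a patient who answers 1 on the other *k* − 1 items (no problem) and 4 on item 47 (fully satisfied). The mean is (*k* − 1 + 4) / *k* = 1 + 3/*k*, so the score is (3/*k*) / 3 × 100 = 100/*k*.

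| *k* | As written | Reversed first |
|---|---|---|
| 2 | 50 | 0 |
| 3 | 33.3 | 0 |
| 4 | 25 | 0 |

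A patient with no other problems who is not at all satisfied shows the mirror image: 0 as written, and 100/*k* (50, 33.3 or 25) after reversal.

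**Standardized response mean.** Take four items, with item 47 always the mirror of the other three. Answers 1, 1, 1, 4 give 25 where the correct score is 0, and 4, 4, 4, 1 give 75 where it is 100. So the score as written equals 25 + 0.5 × the correct score. The mean change and the standard deviation of change are both halved, and their ratio does not change. For item 47 alone, the score as written is 100 minus the correct score, so the ratio keeps its size and changes sign.

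**The case against.** The strongest reply is that the direction sentence describes final scores, not raw answers. If item 47 is reversed before it enters a multi-item scale, the sentence is true as printed. Section 11.3 also reads as a summary rather than a full algorithm. For example, QLQ-C30 items 1 to 28 are all worded as problems, yet high functioning scores are said to be better, so an inversion that is not spelled out must take place there too.

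Part of this stands. The documents do not say that item 47 is left unreversed, so the finding has to be conditional. The QLQ-C30 comparison does not close the gap, however. Where all items in a scale run the same way, a linear transformation of their mean can set the direction. Where one item runs against the others, no transformation of the mean repairs it; that item must be recoded before averaging, and the plan never says so.

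A reader might infer three stronger claims, which the documents do not support:
- **That satisfied patients will be given the worst score.** A score of 100 requires that item 47 stand alone and be left unreversed. Neither is stated.
- **That the error differs between arms because the suggested Arm B regimen includes a seven-day infusion.** The QLQ-HDC29 is completed after initial treatment and before transplant, and again about 100 days after stem cell infusion. The suggested regimens are not mandatory, and Section 7.1 leaves the inpatient or outpatient setting open. Who will be in hospital at those two times is unknown.
- **That the standardized response mean would be halved.** The check above shows that uniform compression cancels in the ratio. In general, the effect inside a scale depends on correlations between items, which the plan does not give.

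**Conclusion.** The point holds as a gap in the scoring specification. Followed literally, Section 11.3 scores item 47 in the wrong direction. The error is a full reversal on the 0–100 scale if the item stands alone. For an otherwise problem-free, fully satisfied patient it is 50, 33.3 or 25 points in a scale of 2, 3 or 4 items. The result rests on two conditions that the documents leave open: that no recoding is applied, and which scale, if any, contains item 47.

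The consequence is limited. It concerns one of 29 module items, answered only by patients still in hospital when they complete the form, at two time points, for a secondary endpoint. Failure-free survival at 18 months is unaffected. No claim is made about imbalance between the arms or about the size of the standardized response mean.

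**What to change.** State in Section 11.3 whether item 47 belongs to a multi-item scale, and then adopt the matching option:

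- **(a) It enters a multi-item scale.** Reverse-code it as 5 minus the response before averaging, and keep item 52 as the only exception to the direction rule.
- **(b) It is reported alone and unreversed.** Name item 47 together with item 52 as exceptions, with a higher score meaning better.

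The two must not be combined. Once item 47 is reversed, a high score does mean worse, and listing it as an exception would introduce a new error. A short item-to-scale list for the QLQ-HDC29 would settle which option applies.

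The cost is one sentence in Section 11.3 and one line of scoring code. No change to data collection is needed.

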12.0 DATA MANAGEMENT/CONFIDENTIALITY

Study data will be stored in a locked cabinet in a building with restricted key-card access. A password protected data recording tool (e.g., excel spreadsheet) will be used to record disease progression, relapse and death for all patients (See Appendix I). Each subject is assigned a unique patient number to assure subject confidentiality. Subjects will not be referred to by this number, by name, or by any other individual identifier in any publication or external presentation.

The licensed medical records department, affiliated with the institution where the subject receives medical care, maintains all original inpatient and outpatient chart documents.

At FHCRC, local subject clinical records and transplant-related documents are scanned and stored in a secure, electronic document management platform (OWL). OWL records are maintained by the FHCRC data abstraction staff. Access is restricted to personnel authorized by the Division of Clinical Research.

13.0 STATISTICAL CONSIDERATIONS

Eligible patients will be randomized in a 1:1 fashion. The primary outcome will be analyzed on an intention-to-treat basis. It is not possible to enroll enough patients to this trial to show a statistically significant difference in overall survival between groups unless the assumed-true difference is unrealistically large. Instead, we have set a benchmark for “success” to be that the observed 18-month failure-free survival with hypomethylating agent-based treatment be at least as high as that in the intensive chemotherapy group. With 30 patients per arm, if the assumed-true survival probabilities are 50% and 30%, respectively, then the probability of observing an 18-month failure-free survival in the HMA group that is at least as high as that in the IC group is approximately 0.96. If the assumed-true probabilities are 45% and 30%, the probability of observing a success is approximately 0.91. On the other hand, if the 18-month failure-free survival in the HMA group and IC group is 50% and 60%, respectively, then the probability of observing a rate in the HMA group that is at least as high as that in the IC group is approximately 0.26.

The quality-of-life questionnaires will be scored. In addition to reporting the absolute scores, a distribution-based interpretation will be conducted using the standardized response mean to analyze changes in scores over time and differences between groups.

**Projected Target Accrual
ETHNIC AND GENDER DISTRIBUTION CHART**

TARGETED / PLANNED ENROLLMENT: Number of Subjects			
Ethnic Category	Sex / Gender		
	Females	Males	Total
Hispanic or Latino	1	1	2
Not Hispanic or Latino	24	34	58
Ethnic Category Total of All Subjects*	25	35	60
Racial Categories			
American Indian / Alaska Native	0	0	0
Asian	0	1	1
Native Hawaiian or Other Pacific Islander	0	0	0
Black or African American	1	1	2
White	24	33	57
Racial Categories: Total of All Subjects*	25	35	60

*The “Ethnic Category Total of All Subjects” must be equal to the “Racial Categories Total of All Subjects.”

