2.0 BACKGROUND

2.1 Study Disease

MDS represents a group of clonal myeloid stem cell disorders with a heterogeneous spectrum of presentation, ranging from an indolent course over several years to rapid progression to acute myeloid leukemia (AML). MDS typically occurs without a preceding insult (*de novo* MDS) but can also occur after chemotherapy or radiotherapy resulting in secondary MDS. The natural history of patients with MDS is varied with a median survival ranging from 5.7 years for patients with low-risk IPSS (International Prognostic Scoring System) scores, to 0.4 years for those with high-risk scores [1]. Although some conventional therapies have been shown to prolong survival, the only treatment modality for MDS with demonstrated curative potential is allogeneic hematopoietic cell transplantation.

With a median age at the time diagnosis of 65 years, the care of patients with MDS is often complicated by medical comorbidities, and treatment considerations revolve around a balance of the benefit and tolerability of a given modality. Historically, transplantation had been reserved for the young and fit with related donors as the intensive conditioning led to high rates of transplant-related mortality. As a result of improved conditioning regimens, prevention of liver toxicity with ursodiol, and improved microbial surveillance, prevention, and treatment with reduced complications from cytomegalovirus and fungal infections HCT outcomes have improved over time [2]. Furthermore, the development of reduced intensity conditioning (RIC) regimens has extended transplantation to patients with increasing age and comorbidities. Currently, over 60% of patients undergoing HCT for MDS are conditioned with a reduced intensity regimen.

Despite the curative potential of HCT, relapse remains the primary cause of failure after transplantation [3-5]. The risk of relapse not only correlates with intrinsic disease properties such as cytogenetics, but also with the total disease burden. Although there is less non-transplant-related mortality with RIC regimens, there is an increase in relapse as compared to conventional high-dose regimens [4,5]. This result is thought to be due to the fact that little disease reduction occurs with reduced conditioning, placing more responsibility on the graft-versus-leukemia effect to clear the disease. This conclusion is supported by the fact that patients with a higher disease burden prior to

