5.0 SUBJECT SELECTION

5.1 Inclusion Criteria

5.1.1 Disease Criteria

1. Diagnosis of *de novo* or secondary MDS, including chronic myelomonocytic leukemia, as defined by the 2008 World Health Organization Classification System.
2. Patients must have measurable disease requiring cytoreduction, defined as a bone marrow myeloblast count $\geq 5\%$ and $< 20\%$ on morphologic examination or by flow cytometry in cases in which adequate morphologic examination is not possible.

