6.0 SUBJECT REGISTRATION

[figure not shown]
[figure not shown]
Complete and submit the FHCRC Research Subject Registration Form (see Appendix A) with the signed informed consent to the FHCRC Research Coordinator, [contact].

After the eligible subjects have been registered, subjects will be randomized by the FHCRC Data Management Office (DMO), Monday through Friday between 8:30 and 4pm PST/PDT. FHCRC Research Coordinator will fax the randomization assignment back to the Study Coordinator at the outside site.

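### The plan names no stratification factor and no baseline-adjusted estimate for the primary comparison, although every eligible patient has a baseline blast count

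*Combined protocol and SAP*

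**What the plan says.** On allocation, Section 13.0 says only that "Eligible patients will be randomized in a 1:1 fashion". Section 6.0 adds that a central data management office makes the assignment. Neither section names a stratification factor, blocking or minimisation.

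On the analysis, Section 13.0 specifies intention to treat. Its criterion of success should "be that the observed 18-month failure-free survival with hypomethylating agent-based treatment be at least as high as that in the intensive chemotherapy group". It gives no margin, interval or covariate adjustment. It explains why there is no formal test: "It is not possible to enroll enough patients to this trial to show a statistically significant difference in overall survival between groups". Its operating characteristics begin "With 30 patients per arm, if the assumed-true survival probabilities are 50% and 30%, respectively", for which it gives 0.96. It continues: "If the assumed-true probabilities are 45% and 30%, the probability of observing a success is approximately 0.91". For true rates of 50% on HMA and 60% on IC it gives 0.26.

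On prognosis, Section 2.1 says: "The risk of relapse not only correlates with intrinsic disease properties such as cytogenetics, but also with the total disease burden".

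On availability, Section 5.1.1 says "Patients must have measurable disease requiring cytoreduction, defined as a bone marrow myeloblast count" of at least 5% and below 20%. Section 7.3 makes the screening marrow mandatory, and Section 11.2 takes it as the disease-burden baseline. Appendix C divides blasts at 10% when it defines progression, and return to the pretreatment blast percentage is one of its criteria for relapse.

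**The concern.** Relapse is half of the primary endpoint, and the protocol links relapse to disease burden. A measure of that burden is in hand for every patient before randomisation, but the plan uses it neither to balance the arms nor to adjust the estimate. The verdict rests on which of two raw rates is higher, with 30 patients per arm, so one patient is worth 3.3 points (1/30).

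The trial will be run once. If one arm happens to receive clearly more high-blast patients, the plan has no pre-specified estimate that takes this into account. Any adjustment chosen after the data are seen would be open to challenge.

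**Working it through.** **Inputs.** Section 13.0 gives 30 per arm, three pairs of true rates and the success rule. Section 5.1.1 gives the blast range and Appendix C the 10% division. The following are assumptions, not in the documents: 30 of 60 patients have 10% blasts or more (high-blast); FFS differs between bands by g = 10, 20, 30 or 40 points, equally in both arms and centred on the arm's overall rate; allocation is simple, with 30 per arm.

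**1. The plan's own figures.** With independent binomials on 30 patients, P(success) = Σ P(X_HMA = x) · P(X_IC ≤ x). This gives 0.959 at 50/30, 0.911 at 45/30 and 0.257 at 50/60. The stated 0.96, 0.91 and 0.26 reproduce, with ties counted as success. At equal rates of 40/40 the result is 0.552.

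**2. How often the arms are unbalanced.** The number K of high-blast patients on HMA is hypergeometric (60 patients, 30 high-blast, 30 drawn). The arms differ by |2K − 30|. P(differ by 4 or more) = 0.44 and P(differ by 6 or more) = 0.196. If 20 or 40 of the 60 are high-blast, the chance of 6 or more is 0.17.

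**3. What an 18 v 12 split does.** It shifts the expected difference by (18 − 12)/30 × g = 0.2g, that is 2, 4, 6 or 8 points. The SE of the raw difference at 40/40 is √(2 × 0.4 × 0.6/30) = 0.126, so even 8 points is about 0.6 of one SE.

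**4. Precision.** With balanced bands at 40/40, the variance per patient falls from 0.24 to 0.24 − g²/4. The ratio 0.24/(0.24 − g²/4) is 1.01, 1.04, 1.10 and 1.20 for the four gaps, equivalent to about 1% to 20% more patients.

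With adjustment alone after simple allocation, the two bands hold 30 patients each, so the Mantel-Haenszel weights are ½ and ½. The balanced variance is multiplied by the mean of 225/[K(30 − K)], which is 1.018. The ratios become 0.99, 1.03, 1.08 and 1.18. If blasts are not prognostic (g = 0), the raw SE at 50/30 is √((0.25 + 0.21)/30) = 0.124, and the adjusted SE is 0.124 × √1.018 = 0.125.

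**5. Probability of success.** Columns 2 to 4 assume perfect balance (15 v 15). The last column is for truly equal arms (40/40) that happen to split 18 v 12.

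| Gap g | 50/30 | 45/30 | 50/60 | 40/40, split against HMA / for HMA |
|---|---|---|---|---|
| Simple allocation, averaged | 0.959 | 0.911 | 0.257 | 0.552 |
| 10 points | 0.960 | 0.912 | 0.255 | 0.489 / 0.615 |
| 20 points | 0.962 | 0.916 | 0.252 | 0.425 / 0.677 |
| 30 points | 0.967 | 0.922 | 0.246 | 0.359 / 0.738 |
| 40 points | 0.973 | 0.931 | 0.237 | 0.291 / 0.799 |

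On average, balance changes P(success) by at most about 2 points (45/30: 0.911 to 0.931; 50/60: 0.257 to 0.237). Given a particular imbalance, its direction matters much more.

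**The case against.** Several points on the other side stand.

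- A reader might infer that the protocol calls baseline blast percentage prognostic. It does not. Section 2.1 speaks of total disease burden, and the evidence it then gives is burden before transplant compared with remission, which is measured after the randomised therapy. Nothing says that 5-<10% and 10-<20% at screening differ in 18-month FFS. The Appendix C bands define progression and are not prognostic groups.
- A reader might infer that chance imbalance undermines the stated probabilities. It does not. They are exact binomial values that already average over every allocation.
- A reader might infer that randomisation is known to be unstratified. The readable text only fails to name a factor.
- Blasts are not the only candidate. Section 2.1 also names cytogenetics, and the trial is multi-centre. Blasts are preferred here because the documents require them on every patient; no section requires cytogenetics at screening.
- The larger weakness is the success rule, which is met about 55% of the time when the arms are equal. Stratifying does not cure that.
- An adjusted estimate merely printed beside the raw rates would leave the verdict unchanged. The fix therefore has to say what happens when the two disagree.

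These points limit the size of the concern. They do not remove the case for naming in advance one adjusted estimate built on a value already collected.

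**Conclusion.** The concern holds as a modest and inexpensive improvement, not as an error in the plan's figures. There is about a 1 in 5 chance of a high-blast imbalance of six or more patients. A six-patient imbalance is worth about 2 to 8 points on the observed difference, against the 10-point deficit in the plan's own 50% v 60% scenario. Stratification is worth about 1% to 20% more patients; adjustment alone ranges from a loss of about 1% to a gain of about 18%.

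All of this rests on an assumed even split at 10% blasts and an assumed 10 to 40-point gap. If the true gap is near the low end, the gain in precision is negligible. What remains then is a pre-specified answer should the arms come out visibly unbalanced.

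**What to change.** In Section 13.0, pre-specify a Mantel-Haenszel difference in 18-month FFS stratified by screening blasts (5-<10% v 10-<20%), with a 95% CI, reported with the raw rates. State that the conclusion will be qualified if the adjusted and raw differences disagree in sign. State the randomisation method in Section 6.0 or 13.0.

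If accrual has not begun, also randomise centrally from two lists on the same split. Because the trial is open-label, use randomly varying block sizes that are not disclosed to sites. The documents do not give accrual status, but the appendices record a 2015 amendment and a 2019 revision, so the analysis change may be the only part still open.

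The cost is a blast field on the registration form (Appendix A) and the data sheet (Appendix H), neither of which has one, plus a second list if randomisation is stratified. No extra patients or procedures are needed. If blasts turn out not to be prognostic, the adjusted estimate is very slightly less precise than the raw one (SE about 0.125 v 0.124).

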3.0 STUDY OBJECTIVES

3.1 Primary Objectives

The primary objective is to determine the effect of IC (intensive AML-like therapy), versus less intensive hypomethylating agents (HMA) as initial therapy, on failure-free survival. We will test the hypothesis that HMA will lead to failure-free survival that is at least as good as that with IC.

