4.2 Endpoints

4.2.1 Primary Endpoint

18-month failure-free survival (failure defined as death or relapse)

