For patients randomized to Arm B, response to therapy will be determined by bone marrow biopsy or aspirate 28 (+/- 3) days after the start of therapy or at the time of count recovery. If a desired response is achieved, the patient may proceed to HCT. If a less-than desired response is achieved with the first cycle of intensive chemotherapy, it is recommended that the patient receive an additional cycle of intensive therapy (re-induction). If after re-induction a partial remission or better is achieved, the patient may proceed to HCT. However, if the patient has stable disease or disease progression, the patient should be offered alternative treatment or proceed directly to transplant if possible. .

If at any point a patient no longer desires to undergo HCT, or is no longer considered an HCT candidate, the patient will be withdrawn from the study. However, the patient may go on to receive the assigned treatment off study protocol.

The number and timing of clinic visits or scheduled inpatient admissions will be determined by either the primary treatment protocol or at the discretion of the attending physician.

Treatment phase evaluations are outlined in the study calendar (Appendix D). After initial treatment and before transplant, complete the EORTC-QLQ-C30 and EORTC-QLQ-HDC29 questionnaires.

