7.7 Criteria for Removal/Withdrawal

A patient must be discontinued from protocol-prescribed therapy under the following circumstances:

- Consent withdrawal at the patient's own request or at the request of their legally authorized representative;
- Any event that, in the judgment of the Investigator, poses an unacceptable safety risk to the patient;
- If, in the investigator's opinion, continuation in the study would be detrimental to the patient's well-being;

- Significant deviation from inclusion/exclusion criteria, in the opinion of the investigator;
- A positive pregnancy test at any time during the study;
- An intercurrent illness that, in the judgment of the investigator, would affect assessments of the clinical status to a significant degree and requires discontinuation of therapy, or
- Completion of the study

Once the attending physician has met and discussed the decision with the patient and/or family member, the Notice of Withdrawal from a Research Study form (see Appendix E) should be filled out. Complete this form only when the patient has withdrawn consent.

- It is the responsibility of the PI or his/her designee to complete the Notice of Withdrawal From a Research Study Form and fax it to the FHCRC Research Coordinator at [contact].

Study treatment is defined as "any activity involving a patient or donor described in a protocol that is not part of their routine medical care". Patients who withdraw from study treatment will be asked permission to continue to collect and record survival data up to the protocol-described end of the subject follow-up period.

Patients who are withdrawn from the protocol will not be replaced as this is intent to treat analysis.

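### Section 3.1 promises a hypothesis test of HMA against IC, but Section 13.0 answers it only with a benchmark on observed rates, which a tie meets and which cannot establish the hypothesis

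*Combined protocol and SAP*

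**What the plan says.** Section 3.1 sets the primary objective as a test: "We will test the hypothesis that HMA will lead to failure-free survival that is at least as good as that with IC". Section 4.2.1 gives the endpoint as "18-month failure-free survival (failure defined as death or relapse").

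Section 13.0 is the only statistical section. It specifies 1:1 randomization, 30 patients per arm and an intention-to-treat analysis of the primary outcome. It then says: "It is not possible to enroll enough patients to this trial to show a statistically significant difference in overall survival between groups", unless the true difference is unrealistically large. The next sentence begins "Instead, we have set a benchmark for" success, and the benchmark is that the "observed 18-month failure-free survival with hypomethylating agent-based treatment be at least as high as that in the intensive chemotherapy group".

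The section gives the probability of meeting this benchmark in three scenarios (HMA vs IC): 0.96 at 50% vs 30%, 0.91 at 45% vs 30%, and 0.26 at 50% vs 60%. Neither Section 13.0 nor any other part of the supplied text names a test, significance level, sidedness, margin or confidence interval for the primary comparison.

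**The concern.** The two sections describe different things. Section 3.1 announces an inference about the true rates. Section 13.0 compares two observed proportions and attaches no measure of uncertainty. As the plan stands, the benchmark is its only answer to the Section 3.1 hypothesis, and nothing says that meeting it leaves that hypothesis unproven.

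What is at stake is how the result is read. Section 1.0 says the results are meant to guide practice. With 30 patients per arm, the benchmark can be met by data that are also compatible with a large deficit on HMA. A reader who takes Section 3.1 at its word could treat a met benchmark as a confirmed hypothesis.

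**Working it through.** **Inputs.** From Section 13.0: n = 30 per arm, success if the observed HMA rate is at least the observed IC rate, and the three pairs of assumed rates. My assumptions: 18-month status is known for all 60 patients; common true rates of 30% to 60% for the equal-rates case (the span of rates in Section 13.0); a two-sided 95% level for the intervals. The plan states no level.

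**Step 1: reproduce the plan's figures.** Let X_H ~ Bin(30, p_H) and X_I ~ Bin(30, p_I), independent. Then P(success) = P(X_H ≥ X_I), the sum of P(X_H = i)·P(X_I = j) over all i ≥ j.

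| True HMA vs IC | Printed | Exact, tie = success | Exact, tie excluded |
|---|---|---|---|
| 50% vs 30% | 0.96 | 0.959 | 0.930 |
| 45% vs 30% | 0.91 | 0.911 | 0.860 |
| 50% vs 60% | 0.26 | 0.257 | 0.181 |

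The printed values are right, and they reproduce only if a tie counts as success.

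**Step 2: what a tie is compatible with.** The observed difference is 0.

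- Wald lower limit: -1.96·√(2p(1-p)/30). At p = 0.50 this is -1.96 × 0.1291 = -0.253.
- Newcombe lower limit: -√((p-l)² + (u-p)²), where l and u are the Wilson limits for one arm. At 15 of 30 the Wilson limits are 0.3315 and 0.6685, so the limit is -√(0.1685² + 0.1685²) = -0.238.

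| Tie at | Newcombe | Wald |
|---|---|---|
| 9 of 30 | -0.223 | -0.232 |
| 12 of 30 | -0.235 | -0.248 |
| 15 of 30 | -0.238 | -0.253 |
| 18 of 30 | -0.235 | -0.248 |

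Each of these ties meets the benchmark, and each is compatible with HMA being more than 20 points worse.

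**Step 3: scenarios the plan does not print.** The formula is that of Step 1.

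- Equal true rates: 0.556 at 30%, 0.552 at 40%, 0.551 at 50%, 0.552 at 60%. By symmetry this is 0.5 plus half the tie probability; at 30%, 0.5 + 0.1121/2 = 0.556.
- HMA truly 5 points worse: 0.386 (25% vs 30%), 0.394 (35% vs 40%), 0.397 (45% vs 50%), 0.396 (55% vs 60%).

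**The case against.** The strongest reply is that the benchmark is a disclosed and deliberate choice. Section 13.0 says significance is out of reach, says a benchmark is used instead, and prints a 0.26 chance of meeting it when HMA is truly 10 points worse. Section 1.0 describes the primary aim more softly, as an assessment of impact. Nothing in the plan forbids reporting an interval, and nothing says that a met benchmark will be presented as proof.

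Most of this stands. There is no miscalculation and no concealment, and a small trial may use a descriptive benchmark. But the concession on significance is worded for overall survival, not for the primary endpoint. Section 3.1 still promises a test, and no sentence tells the reader that the benchmark falls short of one.

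A reader might go further and hold the benchmark to a 95% lower limit of zero. On that standard, 50% vs 30% meets the benchmark 96% of the time but clears the limit only 35 to 36% of the time, and HMA would need a lead of 7 or 8 patients. The documents do not support using this as evidence of a defect. A lower limit at or above zero is in effect a superiority test, and Section 13.0 already disclaims significance. The low figure is what the plan itself would lead one to expect. The interval at a tie makes the point without that standard.

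**Conclusion.** The point holds as a mismatch between the wording of the objective and the criterion that is meant to answer it. It is worth correcting and is not fatal to the trial. With 30 per arm and complete 18-month status, a result the plan calls a success can have a 95% lower limit of about -22 to -25 points, depending on the rate and the method. The benchmark is met about 55% of the time at equal true rates and about 39 to 40% at a true 5-point deficit.

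The 55% should not be read as a type I error rate. It is what a zero threshold on observed rates gives when the arms are equal, and the plan claims no error control. Nor do these figures show that the trial needs more patients or a formal non-inferiority design; the plan does not claim to be one.

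A reader might also infer that relapse status will be lost after withdrawal. Section 7.4 says that a patient who no longer desires transplant "or is no longer considered an HCT candidate, the patient will be withdrawn from the study", and Section 7.7 says "Patients who withdraw from study treatment will be asked permission to continue to collect and record survival data". The documents do not settle this. Section 8.0 plans tracking of progression and survival through 18 months, Section 12.0 plans recording of progression, relapse and death for all patients, and Appendix D lists relapse at 18 months, although none of them expressly covers withdrawn patients. How unknown status is counted is a separate point and should be raised on its own. Here it enters only as the assumption that status is known for all.

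**What to change.** Keep 60 patients, the endpoint, the follow-up and the benchmark. Change three pieces of text.

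- **Section 3.1:** reword as estimation. For example: to estimate the difference in 18-month failure-free survival between HMA and IC, and to describe whether the observed HMA rate meets the Section 13.0 benchmark.
- **Section 13.0, primary report:** make it the difference in 18-month failure-free survival with a 95% confidence interval by a method named in advance, for example Newcombe.
- **Section 13.0, interpretation:** state that meeting the benchmark alone does not establish that HMA is at least as good as IC.

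Optionally, print the success probability at equal rates (about 0.55) and at a 5-point deficit (about 0.39 to 0.40) beside the three existing scenarios.

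The cost is a few sentences and one interval. The downside is a more modest headline: a success at a tie would be reported beside an interval of roughly plus or minus 22 to 25 points.
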